Of our first cohort of patients, 19% of patients underwent biopsy after a positive PSMA PET imaging. Based on biopsy results there was 100% sensitivity and 87% specificity. There were no True Negatives or False Negatives on biopsy. Imaging follow-up is not complete for our first study so we cannot estimate the percent of patients that will have imaging follow-up, but it appears that roughly 15 to 20% of patients will have imaging follow-up. Consistent with our second protocol, we anticipated that the sensitivity for the four regions and for all regions combined using conventional imaging ranges from 30-60%. An overall sensitivity for ^{68}Ga -PSMA-11 PET of at most 50% will be considered as unacceptably low. Hence, the null hypothesis that the sensitivity is at most 50% will be tested against the alternative hypothesis that the sensitivity is greater than 50%. It is hypothesized that ^{68}Ga -PSMA-11 PET imaging on the per-region and per-patient basis will substantially increase the sensitivity for the four regions to at least 70%. A sample size of 75 true positives is required for rejecting the null hypothesis that the sensitivity is at most 50% with 90% power at the one-sided 0.01 ($=0.05/5$ – a Bonferroni adjustment for evaluating the sensitivity for the four regions and for all regions combined) significance level, assuming an average regions specific prevalence of 20%. Although 19% of patients underwent biopsy and 15% of patients have imaging follow-up, we anticipate that the biopsy rate will fall in this study as referring clinicians become more comfortable with the imaging results. Therefore, we will combine imaging and biopsy follow-up in the primary aim, and will require 375 with both imaging and/or biopsy follow-up in order to power the analysis at a per region level. Assuming a prevalence rate of 20% for disease in each individual region, a total sample size of 1,500 patients is required. In summary, the proposed target accrual of 1,500 patients (375 with biopsies or imaging follow-up) will provide adequate power for detecting the anticipated improvement in the sensitivity for both the per-patient and per-region based ^{68}Ga -PSMA-11 PET imaging. However, a sample size of 107 patients with biopsies/follow-up in total is sufficient for detecting the anticipated improvement in sensitivity when evaluating per-patient based sensitivity.

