8.3.2 Analysis of Primary Endpoints

Sensitivity on a per-patient and per-region-basis of ^{68}Ga -PSMA-11 PET for detection of tumor location confirmed by histopathology/biopsy, clinical and conventional imaging follow-up will be calculated and reported along with the corresponding two-sided 95% confidence intervals. The confidence intervals will be constructed using the Wilson score method. For successful completion of the primary endpoint, two of the three readers will need to have an 70% sensitivity for the detection of disease on a per patient level for the cases that have a) imaging follow-up, b) pathology correlation or c) combination of pathology and imaging follow-up and/or pathology correlation.

^{68}Ga -PSMA-11 PET Results Definition

a) Imaging interpretation ^{68}Ga -PSMA-11 PET:

Local Interpretations: PET images will initially be interpreted by a board certified nuclear medicine physician or a board-certified radiologist experienced in reading PET at the time of the imaging study at the institution that the study is being performed. These interpretations will not be used for final evaluation, and will not be reported as part of the primary or secondary endpoints.

Central Read Logistics: Imaging data will be anonymized and collected at a central site. PET data will be interpreted by three different readers in a random order at separate reading sessions. Cross sectional imaging (CT or MRI) from the ^{68}Ga -PSMA-11 PET will be available for anatomic correlate. The Central readers will be blinded to all other imaging results and all other clinical data.

Reader Positivity and Negativity Definition: Regions defined in Table 1 will be graded for the presence of suspected disease on a two-point scale by each reader (0=Negative or 1=Positive). A region will be judged as positive if at least one lesion in this region is visually positive.

Reader Training: ^{68}Ga -PSMA-11 PET/CT reading training set and guides will be provided and completion of this training will be required for all central review readers. Common pitfalls will be reviewed as part of the reader training.

Criteria for visual interpretation:

Regions of suspected disease will be graded on a two-point scale by each blinded reader (0=Negative or 1= Positive). A region will be judged as positive if at least one lesion in this region is visually positive.

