- For patients undergoing systemic treatment (alone or in combination with targeted treatment): If on post-treatment follow-up imaging within 3-12 months, lesions seen on CT or MRI increase by more than 20% in long axis diameter and PSA decreases by more than 50%.

- In subjects with localized suspected lesions(s) receiving targeted treatment without concomitant systemic treatment there are two ways to meet false positive disease:

- If the subject does not demonstrate a decrease of PSA by greater than 50% after targeted treatment [OR]
- If on post-treatment follow-up imaging within 3-12 months, lesions seen on CT or MRI increase by more than 20% in long axis diameter (with a minimum of 3 mm in change in size)

- For untreated patients: If on follow-up imaging within 3-12 months, lesions seen on CT or MRI decrease by more than 30% in long axis diameter (with a minimum of 3 mm in change in size).

(3) If the lesion does not meet criteria for either True positive or False positive disease, then the lesion will be considered inevaluable for primary endpoint.

c) Histopathology/Biopsy:

- i) ⁶⁸Ga-PSMA-11 positive findings are aimed to be confirmed by histopathology/biopsy if clinically feasible. Pathology performed 60 days before the PSMA PET will be available for correlation.
- ii) Histopathological procedures and biopsies will be performed as clinically indicated and as per institutional protocol.

(1) Positive Histopathology/Biopsy: Confirmed sites of metastatic or tumor involvement by histopathology/biopsy will be discussed with the responsible physician/surgeon.

- (a) True Positive: lesion is positive on targeted biopsy/surgical sampling and is read as positive on PSMA PET.
- (b) False Negative: lesion is positive on targeted biopsy/surgical sampling and is read as negative on PSMA PET.

- (2) **Negative Biopsy:** Patients with suspected tumor recurrence on ^{68}Ga -PSMA-11 PET with negative histopathology/biopsy will be handled as outlined below:
- (a) Lymph nodes:
- For patients undergoing nodal dissection: Patients will be rescanned with dedicated CT, MRI or a repeat ^{68}Ga -PSMA-11 PET to determine if the suspicious ^{68}Ga -PSMA-11 positive node was removed.
 1. If ^{68}Ga -PSMA-11 positive lymph node is still present, a repeat biopsy can be pursued if clinically feasible and applicable, or follow-up using imaging as described above will be performed.
 2. If the corresponding node was removed, then this will be considered a False Positive.

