- (2) True negative patient: in the absence of True Positive or False Positive lesions, a patient will be considered a True Negative if there is pathology that is negative for disease and corresponding lesion is negative by PSMA PET.
 - (3) False positive patient:
 - (a) Pathology confirms a false positive lesion that is read as positive on PSMA PET.
 - (b) In the absence of pathology: there are no true positive regions, and there is a region that is categorized as false positive based on imaging or clinical follow-up.
 - (4) False negative patient: in the absence of True Positive or False Positive lesions, a patient will be considered a False Negative if there is pathology that is positive for disease and corresponding lesion is negative by PSMA PET. Additionally, patients without evidence of disease on PSMA PET but with biochemical evidence of disease will be considered a False Negative.
- ii) Region level evaluation: Each patient will have four evaluable regions (Table 1: prostate bed, pelvis, extrapelvic soft tissue, and bone metastases). Each region will be categorized as true positive or false positive as described above. Regions without evidence of PSMA positive disease or deemed inevaluable will not be included in the analysis.
 - (1) True positive region:
 - (a) Pathology confirms a PSMA avid lesion as a true positive in the region.
 - (b) In the absence of pathology, clinical or imaging follow-up demonstrates a true positive lesion within the region independent of the presence of an inevaluable lesion or a false positive lesion
 - ie true positive disease will supersede a false positive lesion in the region based analysis if based on imaging/clinical follow-up
 - (2) True negative region: in the absence of True Positive or False Positive lesions within a region, the region will be considered a True Negative if there is pathology that is negative for disease in the region and corresponding lesion is negative by PSMA PET.
 - (3) False positive region:
 - (a) Pathology confirms a PSMA avid lesion as a false positive in the region

- (b) In the absence of pathology, there are no true positive lesions in the region, and there is a false positive lesion by clinical or imaging follow-up.
- (4) False negative region: in the absence of True Positive or False Positive lesions in a region, the region will be considered a False Negative if there is pathology that is positive for disease in the region and corresponding lesion is negative by PSMA PET.

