8.3.3 Analysis of Secondary Endpoints

1. PPVs on a per-patient and per-region-basis of ^{68}Ga -PSMA-11 PET for detection of tumor location confirmed by histopathology/biopsy, clinical and conventional imaging follow-up will be calculated and reported along with the corresponding two-sided 95% confidence intervals. The confidence intervals will be constructed using the Wilson score method. PPV will be reported for each of the three blinded readers independently.
2. Sensitivity and PPVs on a per-patient and per-region basis of ^{68}Ga -PSMA-11 PET for detection of tumor location confirmed by histopathology/biopsy will be summarized in tabular format. Ninety-five percent confidence intervals of sensitivity, specificity, NPV and PPV will be calculated using the Wilson score method. These will be reported for each of the three blinded readers.
3. Detection rates on a per-patient basis of ^{68}Ga -PSMA-11 PET stratified by PSA value (0.2 - <0.5, 0.5 - <1.0, 1.0 - <2.0, 2.0 - <5.0, ≥ 5.0) will be summarized in tabular format and compared between PSA strata using chi-square analysis. Detection rate will also be stratified by history of prostatectomy, radiation or both; as well as by whether the patient is on androgen deprivation therapy (ADT). We will use local interpretations for this analysis.
 - a. Detection rate is defined as number of patients with PSMA positive disease, independent of pathology, imaging or clinical follow-up. A detection rate will be reported for each reader independently stratified by PSA.
4. The impact of ^{68}Ga -PSMA-11 PET on clinical management in BCR patients will be evaluated using descriptive statistics.
5. Inter-reader reproducibility for positivity at the patient level and region level will be reported using the Fleiss' Kappa test for multiple readers. We will use the three blinded reads for this analysis.
6. Safety will be reported descriptively as rates of patient reported adverse events. Additionally, adverse events will be characterized and quantified by CTCAE 4.03.

9 Study Management

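### The region rules conflict on whether PET-negative regions count; applied as written, the exclusion sentence fixes per-region sensitivity, part of the primary endpoint, at 100%

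*Combined protocol and SAP*

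**What the plan says.** Sections 2.1, 8.1, 8.2.1 and 8.3.2 all make sensitivity, per patient and per region, the primary measure. There are four regions: prostate bed, pelvis, extrapelvic soft tissue and bone.

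Section 8.3.2 d) ii) sets the region rules. Its opening paragraph says "Each region will be categorized as true positive or false positive as described above", and then "Regions without evidence of PSMA positive disease or deemed inevaluable will not be included in the analysis".

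The numbered items below that paragraph define four categories. Item (2) defines a true-negative region. Item (4) says "the region will be considered a False Negative if there is pathology that is positive for disease in the region" and the corresponding lesion is PET-negative. The title of part d) also names all four categories for regions as well as patients.

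Related text elsewhere:
- 8.3.2 c) defines a false-negative lesion: "lesion is positive on targeted biopsy/surgical sampling and is read as negative on PSMA PET".
- 8.3.2 c) also states the aim of tissue sampling: PSMA-"positive findings are aimed to be confirmed by histopathology/biopsy if clinically feasible".
- 8.3.3 item 2, for the histopathology-only analysis, plans that "confidence intervals of sensitivity, specificity, NPV and PPV will be calculated using the Wilson score method".
- 8.3.2 declares success per patient: "two of the three readers will need to have an 70% sensitivity for the detection of disease on a per patient level".

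**The concern.** Sensitivity needs diseased, test-negative cases in its denominator. The opening paragraph of d) ii) removes every PET-negative region, and items (2) and (4) put the pathology-verified ones back. Two analysts could follow the section in good faith and report different regional sensitivities from the same data, one of them fixed at 100%.

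Settling the wording in favour of item (4) leaves a second problem. A region can become a true positive through pathology or through imaging or clinical follow-up, but it can become a false negative only through pathology. The follow-up criteria in 8.3.2 b) classify PSMA-positive lesions only, and biopsy is aimed at such lesions. Dissection, surgical sampling and pathology obtained before PET can reach PET-negative tissue, but nothing makes verification equal on the two sides.

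In section 8.2.1 the four regions account for four of the five Bonferroni-adjusted tests. The regional analysis is also the stated reason for 375 verified and 1,500 enrolled patients; 107 verified patients are said to suffice per patient. Section 1.1 says the data are to be pooled for an NDA submission.

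**Working it through.** **Inputs (section 8.2.1).** Null sensitivity 0.50, alternative 0.70, power 90%, one-sided alpha 0.05/5 = 0.01, regional prevalence 20%, 75 per region, 375 verified patients, 1,500 enrolled. The documents give no verification rate for PET-negative regions.

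**1. The plan's own figure.** With the normal approximation for one proportion,

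n = [(z0.99·√(0.5·0.5) + z0.90·√(0.7·0.3)) / 0.2]² = [(2.326·0.5 + 1.282·0.458) / 0.2]² = 76.6, so 77.

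The plan has 75, which is close enough. Also 75/0.20 = 375, and 375/1,500 = 25%. The sample-size arithmetic is not at issue. The plan says "A sample size of 75 true positives is required for rejecting the null hypothesis", but the test needs 75 diseased regions (TP + FN), and 375 × 0.20 = 75 gives exactly that number. The calculation therefore presupposes a denominator that includes false negatives.

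**2. Opening paragraph governs.** FN = 0 by rule, so Se = TP/(TP + 0) = 1.
- The exact one-sided p-value for n of n against 0.5 is 0.5^n. For n = 6 it is 0.0156, and for n = 7 it is 0.0078, below 0.01.
- With 75 diseased regions, the chance of at least 7 true positives exceeds 0.9999 at a true sensitivity of 50%, and also at 30%. The nominal error is 0.01.
- A result of 75/75 has a Wilson 95% interval of 95.1% to 100%.

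**3. Item (4) governs.** Let r = P(verified | diseased, PET-negative) / P(verified | diseased, PET-positive). Then

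apparent Se = Se / [Se + (1 − Se)·r].

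| Assumed r | True 30% | True 50% | True 70% |
|---|---|---|---|
| 1.00 | 30.0% | 50.0% | 70.0% |
| 0.50 | 46.2% | 66.7% | 82.4% |
| 0.25 | 63.2% | 80.0% | 90.3% |
| 0.10 | 81.1% | 90.9% | 95.9% |

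A true 50% looks like the hoped-for 70% when 0.5/(0.5 + 0.5r) = 0.70, that is, r = 0.43.

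**4. Effect on the regional test.** Assume 75 reference-positive regions and an exact binomial test. The rule at one-sided 0.01 is to reject if X ≥ 49 (size 0.0053). If the true sensitivity is 50%, the probability of rejection is:
- r = 1: 0.0053
- r = 0.50: 0.648
- r = 0.25: 0.999

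**The case against.** The strongest reply is that this is a drafting slip, not a plan to compute TP/TP. The title of part d) assigns all four categories to regions, and items (2) and (4) would be pointless if the opening paragraph cancelled them. A natural reconciliation is that PET-negative regions without pathology are excluded and those with pathology follow items (2) and (4). This is probably what was meant, but it is not written, and the sentence before the exclusion admits only true and false positives. The leeway in part d) to deviate in individual patients does not define a denominator.

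Other points stand in part:
- The contradiction rests on d) ii) itself. The false-negative lesion in 8.3.2 c) also feeds the patient rules, and PET-negative patients could supply the specificity and NPV in 8.3.3. Those texts are supporting evidence only.
- Even under the exclusion, one case is not clearly covered: a region with an inevaluable PET-positive lesion and a separate PET-negative, pathology-positive lesion. The opening paragraph gives it no category.
- Section 8.3.1 limits the primary aim to patients with histopathology, and 8.2.1 opens the same way. If that prevailed, the follow-up asymmetry would go and only differential biopsy would remain. But 2.1, 8.3.2, the later text of 8.2.1 and item (1)(b) of the region rules all admit imaging or clinical follow-up.
- The ratios r are assumed, and 8.2.1 names no test. Step 3 shows the direction and possible size of the bias; it does not measure it. Step 2 needs no such ratio.
- The success rule is per-patient, and the patient rules have no such exclusion: they count PET-negative patients with biochemical disease as false negatives.

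**Conclusion.** The concern holds. Section 8.3.2 d) ii) contains two incompatible rules for the denominator of a primary measure, and no other text decides between them.

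Under the exclusion sentence, regional sensitivity is 100% by construction and carries no information. Under item (4) it can be estimated, but it is biased upward whenever PET-negative diseased regions are verified less often than PET-positive ones (r below 1). The plan neither quantifies nor addresses that bias. Its size depends on r: across the assumed range 0.10 to 0.50, a true 50% appears as 91% down to 67%.

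The defect does not decide trial success as declared. It does undermine the regional half of the primary result and the regional reasoning behind the enrolment target. It must be corrected, and before regional results are known, so that the choice of rule cannot depend on the data.

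**What to change.** 1. In d) ii), limit the exclusion to unverified or inevaluable regions (or to the PPV analysis), and have the preceding sentence list all four categories.
2. State that every pathology-positive region read as PET-negative enters the per-region sensitivity denominator as a false negative.
3. Report the number of verified PET-negative regions for each of the four regions.
4. Add a verification-bias sensitivity analysis over a stated range of r, for example 0.10 to 1.0. The planned data cannot estimate r, so a range is needed.
5. If lesions found on follow-up imaging in PET-negative regions are counted as false negatives, make that analysis supplementary only, because missed lesions cannot be told apart from new ones.

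As a minor separate correction, relabel the pilot 87% specificity in 8.2.1. With no true negatives, specificity is 0/(0 + FP) = 0.

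The cost is SAP wording, one table and one added analysis, with no new patients or procedures. The supplementary analysis may need extra local reads where sites supply only reports. Reported regional sensitivity may fall below 100%, its interval will widen, and some verification bias will remain.

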8.1.2 Blinding

- For primary endpoint analysis of ⁶⁸Ga-PSMA-11 PET imaging studies central readers will be fully blinded to clinical information and any conventional imaging results. Central readers will have access to the concomitant CT or MRI used for attenuation purposes.
- For local interpretation of ⁶⁸Ga-PSMA-11 PET imaging studies, local readers will be unblinded to both clinical information and other conventional imaging data.
- For local interpretation of conventional imaging follow-up images 3-12 months post ⁶⁸Ga-PSMA-11 PET scan, local readers will be unblinded to all results and will be specifically informed of the location of ⁶⁸Ga-PSMA-11 PET positive lesions so that follow-up measurements may be performed on these lesions.

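### Per-region sensitivity: follow-up can make a region true positive but not false negative, so disease that PET missed and follow-up later shows is not counted and the regional estimates are biased upward

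*Combined protocol and SAP*

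**What the plan says.** Sections 2.1 and 8.1 make sensitivity primary both per patient and per region. The reference standard in sections 2.1 and 8.3.2 combines histopathology with clinical and conventional imaging follow-up.

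**Region true positive, 8.3.2 d) ii) (1).** Pathology can establish it, and so can follow-up alone: "In the absence of pathology, clinical or imaging follow-up demonstrates a true positive lesion within the region".

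**Region false negative, 8.3.2 d) ii) (4).** If the region holds no true or false positive lesion, "the region will be considered a False Negative if there is pathology that is positive for disease in the region" and PET was negative at that site. No other route is given.

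**Follow-up rules, 8.3.2 b).** These classify PSMA-positive lesions only, as true positive, false positive or inevaluable. Section 8.1.2 has local readers told where the PET-positive lesions lie, "so that follow-up measurements may be performed on these lesions".

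**Lead-in to 8.3.2 d) ii).** Regions that are PSMA-negative or inevaluable are left out of the analysis. The false-negative and true-negative region definitions just below it need such regions to be kept.

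**Patient level, 8.3.2 d) i) (4).** A patient is false negative by positive pathology at a PET-negative site or, with no pathology needed, by having no disease on PET despite biochemical evidence of disease.

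**Testing, 8.2.1.** For the four regions and overall, "the null hypothesis that the sensitivity is at most 50% will be tested against the alternative hypothesis" of a higher value, "with 90% power at the one-sided 0.01" level, with 70% as the hypothesised sensitivity.

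**The concern.** Sensitivity is detected disease divided by detected plus missed disease. Here two verification routes feed the detected count and only one feeds the missed count. If PET calls the pelvis negative and a follow-up CT shows a new pelvic node, the region has no rule that makes it a miss.

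Pathology is unlikely to close the gap. Section 8.3.2 c) directs confirmation mainly at PSMA-positive findings. Section 8.2.1 expects the biopsy rate to fall, and for that reason brings imaging follow-up into the primary aim. The one-sided route thus becomes the more important one.

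The regional tests are at stake. They take four of the five Bonferroni shares and set the 375 followed and 1,500 enrolled patients; section 8.2.1 says 107 followed patients would do for the per-patient question. The data are meant to support an NDA (section 1.1).

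**Working it through.** **1. The plan's own figure.** Inputs from 8.2.1: null 0.50, alternative 0.70, one-sided 0.01, power 90%, regional prevalence 20%.

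n = [(2.326 × √(0.5 × 0.5) + 1.282 × √(0.7 × 0.3)) / 0.2]² = 76.6, or 77 rounded up.

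The plan states "A sample size of 75 true positives is required for rejecting the null hypothesis", which agrees within two units. Normal-approximation power at 75 is 89.3%, and 75 / 0.20 = 375. The prevalence step shows that the 75 are diseased regions, whatever PET called them. An exact binomial test on 75 regions needs 49 or more detected: its size is 0.5% at a true 50%, and its power is 84.3% at 70%.

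**2. Effect of the false-negative rule.** Let s be true regional sensitivity and f the chance that a missed diseased region is counted relative to a detected one.

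Apparent sensitivity = s / (s + (1 − s) × f). At s = 0.50 this is 1 / (1 + f).

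**3. Values of f.** The documents give none, so f is an assumption. One benchmark uses the rates in 8.2.1: 19% biopsied and 15% to 20% with imaging follow-up, taken as non-overlapping. Detected disease is verified by either route (34% to 39%). Missed disease is verified by biopsy only, assumed as frequent as for detected disease (19%). Then f = 19/34 = 0.56 to 19/39 = 0.49.

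| f | Apparent sensitivity, true 50% | Chance of rejecting the 50% null, 75 counted regions |
|---|---|---|
| 1 (misses counted equally) | 50% | 0.5% |
| 0.56 | 64% | 47% |
| 0.49 | 67% | 69% |
| 0.43 | 70% | 84% |
| 0.25 | 80% | over 99% |
| 0 | 100% | 100% |

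Of 75 diseased regions, only 75 × (0.5 + 0.5f), about 58 to 56, would be counted at f = 0.56 to 0.49. With those smaller counts the chance of rejection is about 37% to 52%. A true sensitivity of 60% would read as 73% to 75%.

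Overlap between biopsy and imaging raises f and shrinks the bias. If only 375/1,500 = 25% are verified by either route, f = 19/25 = 0.76 and a true 50% reads as 57%. Biopsying missed disease less often than detected disease lowers f and enlarges the bias.

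**4. The exclusion sentence.** If PSMA-negative regions are dropped, pathology-proven misses go too. The denominator then holds only true positives, which is f = 0 and 100% at any s.

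**5. Patient level.** Section 8.2.1 expects 24% of patients to be PET-negative, and section 3.3.1 requires biochemical recurrence, so in effect each such patient is a false negative.

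- Within 375 followed patients: 0.24 × 375 = 90 false negatives. If all PET-positive patients are true positive, 285/375 = 76%. If 87% are, 248/338 = 73%.
- If all 0.24 × 1,500 = 360 PET-negative patients count against at most 375 true positives: 375/735 = 51%, or 326/686 = 48% with the 87% figure.

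The 87% is what 8.2.1 calls specificity. It is used here as the true-positive share because that cohort had no true negatives.

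**The case against.** Three points deserve weight.

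**The success criterion is per patient.** A reader might infer that composite sensitivity as a whole, and with it the trial's success rule, is driven towards 100%. The documents do not support that. Section 8.3.2 requires 70% per patient in two of three readers, and the patient rule charges wholly PET-negative patients to PET without pathology. Step 5 gives 48% to 76%, depending on which PET-negative patients enter. No 70% success threshold is set for regions; they are tested against 50%. This objection stands and confines the point to regions, apart from one narrow gap: a patient whose PET-positive lesions are all inevaluable and whose missed disease appears only on follow-up imaging.

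**The size is assumed.** A reader might take "There were no True Negatives or False Negatives on biopsy" as evidence that f is zero. Those biopsies followed a positive PET, so they do not measure how often missed regions reach pathology. This also stands: 80% and 100% are illustrations, not predictions, except that 100% does follow if the exclusion sentence is applied literally.

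**The rules leave some room.** Section 8.3.2 d) calls its criteria a guide and allows recorded deviations. Section 8.1.2 does not confine local readers to PET-positive sites. Section 8.3.2 c) admits clinically indicated pathology and defines a false-negative lesion. So it would be too strong to say that an imaging-shown miss can never be counted. But discretion case by case is not a prespecified rule, and no text tells anyone to look for or classify such disease.

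**Conclusion.** The point holds for the per-region primary endpoint. As written, follow-up can add to the detected count and not to the missed count, so regional sensitivity is biased upward. The direction follows from the text; the amount depends on f.

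On the benchmark assumptions (missed disease biopsied as often as detected disease, the two follow-up routes not overlapping), a region at the 50% null reads as 64% to 67%. It rejects that null 47% to 69% of the time with 75 counted regions, against 0.5% for an unbiased count. Overlap between the routes would make this smaller; fewer biopsies of missed disease would make it larger.

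The exclusion sentence in d) ii) is the more severe defect if applied literally, and it contradicts the definitions beneath it. Per-patient sensitivity and the 70% success rule are largely unaffected.

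**What to change.** 1. Delete or amend the exclusion sentence in the lead-in to 8.3.2 d) ii), so that PET-negative regions with disease on the reference standard enter the sensitivity denominator, as the plan's false-negative and true-negative region definitions require. Without this, step 2 has no effect.
2. Add to d) ii) (4): or, in the absence of pathology, a region read negative on PSMA PET in which conventional imaging at 3 to 12 months shows a new lesion, or growth of a lesion visible at baseline. In untreated patients use the existing untreated growth criterion or the existing new-bone-lesion criterion. In treated patients apply the existing treatment-specific true-positive criteria; otherwise the region is inevaluable. Naming new lesions separately matters because they have no baseline from which to compute a percentage increase.
3. Apply the same rule in d) i) (4) only where the patient has no true-positive or false-positive lesion and all PET-positive lesions are inevaluable.
4. Have local readers record all four regions on the follow-up scans, not only the PET-positive sites.
5. Report a sensitivity analysis that limits imaging false negatives to the earliest follow-up scan.

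The cost is protocol wording and a case report form field on scans already being read; no extra imaging is needed. Regional sensitivity will come out lower. Some late lesions may have arisen after PET, which step 5 helps to bound. Disease that conventional imaging also misses will stay uncounted, so the bias is reduced rather than removed.
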